1.0 PROTOCOL SUMMARY AND/OR SCHEMA

This is a phase 2, open-label, non-randomized study evaluating the novel combination of pembrolizumab and olaparib (POLAR) for maintenance therapy in three cohorts of metastatic PDAC patients with homologous recombination deficiency (HRD) in the first-line or second-line on-platinum setting; two cohorts are genomically enriched and one cohort is identified by platinum sensitivity. The primary endpoint of this study is to evaluate the co-primary endpoints using either 6-month progression-free survival (PFS) rate and objective response rate (ORR) of this combination. The secondary endpoints of this study are overall survival (OS), progression-free survival (PFS), disease control rate (DCR), CA 19-9, and CEA response. Statistically powered analysis of co-primary endpoints will be assessed in Cohort A only and other clinical endpoints will be descriptive in Cohort B and C. Exploratory scientific correlates include assessments of HRD genetic mutational signatures, neoantigens, immunogenic tumor microenvironment, and clonal evolutionary dynamics to study heterogeneity and resistance mechanism to POLAR.

Patients will be assigned to cohorts. Cohorts will be defined as following by CLIA-approved NGS or MSK-IMPACT Part A or C:

[figure not shown]
- **Cohort A**: Patients with either pathogenic germline or somatic alterations of 3 core homologous recombination-genes (HR-genes) (*BRCA1/2*, or *PALB2*) who have stable or responding disease on first-line or second-line platinum therapy in two consecutive imaging assessments over at least 4 months or 16 weeks are eligible for inclusion in Cohort A.
- Cohort B: Patients with either pathogenic somatic or germline non-core 15 HR-gene alterations (ATM, BAP1, BARD1, BLM, BRIP1, CHEK2, FAM175A, FANCA, FANCC, MUTYH, NBN, RAD50, RAD51, RAD51C, RTEL1) who have stable or responding disease on first-line or second-line platinum therapy in two consecutive imaging assessments over at least 4 months are eligible for inclusion in Cohort B.

POLAR: a phase 2 trial for pembrolizumab and olaparib maintenance for metastatic PDAC and HRD and/or Exceptional Response to Platinum – Ver. 5/3/2020

• Cohort C: Patients without any of the above HR-gene alterations included in Cohort A and B who have platinum-sensitivity, which is defined as durable response of either a partial response (PR) or complete response (CR) during at least 6 months on platinum-based therapy. Variants of unknown significance of candidate HR-genes from Cohort A or B will be eligible for Cohort C if they meet the partial response to platinum criterion.

All the participating patients will receive the combination of pembrolizumab 200 mg IV every 3 week and olaparib 300 mg twice day orally daily continuously (POLAR) as a maintenance therapy. After the first 6 months (9 cycles), on C10D1 Pembrolizumab 400 mg IV every 6 week plus olaparib 300 mg twice a day orally will be continued. Per treating investigator's discretion, patients may remain at Pembrolizumab 200 mg IV every 3 weeks after the first 9 cycles. Additionally, to accomodate patients traveling far distances, if, per treating investigator, after the first or second imaging, there are no toxicities, patient's dosing of Pembrolizumab may change to 400 mg IV every 6 weeks. All cycles will be 21-days (3 weeks) in length.

Figure 1. Schema for Genetic and Response Eligibility Criteria:

Number of trial participants	63 (Cohort A: 33, Cohort B: 15, Cohort C: 15)
Estimated enrolment period	3 years
Estimated duration of trial	7.5 years
Duration of Participation	4 years

Estimated average length of	4 months
treatment per participant	

2.0 OBJECTIVES AND SCIENTIFIC AIMS

Primary Objective:

- For Cohort A: To evaluate the activity of pembrolizumab and olaparib (POLAR) combination by co-primary endpoints using either radiographic 6-month PFS rate by RECIST v1.1 and ORR using iRECIST in metastatic pancreas adenocarcinoma (PDAC) patients with core HR-gene mutations.
- For Cohort B and C: To exploratively evaluate the activity of POLAR combination by radiographic ORR using RECIST 1.1.

Secondary Objectives:

- To assess the safety of POLAR by grading adverse events (AE) using CTCAE v. 5.0.
- To assess activity of POLAR by measuring disease control rate (DCR) by both RECIST v1.1 and iRECIST, best overall response rate (BOR), progression-free survival (PFS) by both RECIST v1.1 and iRECIST, overall survival (OS), CEA, and CA 19-9 response. Progression-free survival (PFS) will be analyzed from both the consent date and treatment start date (C1D1) (Reference study POLO defined PFS from the time of randomization not from C1D1, Golan 2019 NEJM).

Exploratory Objectives:

- To explore genetic and transcriptomic signatures for POLAR sensitivity and resistance from HRD Cohort A and B as well as from the platinum-sensitivity Cohort C.
- To describe neoantigen induction, the immunogenic tumor microenvironment (TME), and describe putative immunomodulatory targets from each cohort.
- To explore resistance mechanisms and the role of spatiotemporal heterogeneity by evaluating the tumor samples and circulating tumor DNA (MSK-ACCESS)
- To develop a biorepository of organoids and prospectively evaluate organoids concurrently with the trial in select patients.
- To assess second progression-free survival (PFS2) from time of subsequent systemic treatment start post-POLAR to progression on that treatment.
- To assess duration of the first-line or second-line treatment prior to POLAR treatment.
- To assess genetic signatures and compare clinical outcomes (ORR, PFS, OS) for patients with PDAC harboring specific HRD-gene mutations such as BRCA1, BRCA2, PALB2, ATM, and no HRD-gene mutation.
- To assess the association of other non-HRD gene mutations (such as KRAS allelic imbalance, TP53, SMAD4, CDKN2A homozygous deletion) with the clinical outcomes.
- Evaluate reversion mutation, zygosity, plasticity, and aneuploidy from tumor and circulating tumor DNA.

Confidential

POLAR: a phase 2 trial for pembrolizumab and olaparib maintenance for metastatic PDAC and HRD and/or Exceptional Response to Platinum – Ver. 5/3/2020

 To assess the role of maintenance treatment with minimally residual disease by the presence of circulating tumor DNA and CA 19-9 and its trend prior to treatment at time points prior to consent and between the consent and start date.

7

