All the participants will be enrolled on #12-245 and #06-107 outside of this trial which will allow identification of which Cohort the patient will be assigned to and to permit future biospecimen use for research. Patients have a germline or somatic HR-gene alterations identified in an external CLIA or FDA-approved NGS panel including but not limited to, FoundationOne, Myriad, or Tempus, will be eligible. After enrollment, we will retrospectively confirm their HR-gene alteration status from both germline and somatic MSK-IMPACT profiling.

Study Endpoints:

POLAR: a phase 2 trial for pembrolizumab and olaparib maintenance for metastatic PDAC and HRD and/or Exceptional Response to Platinum – Ver. 5/3/2020

- 1
- Primary endpoint: co-primary endpoints using either 6-month PFS rate by RECIST v1.1 and ORR by iRECIST as Figure 1. Schema.
- Secondary endpoints: disease control rate (DCR) by both RECIST v1.1 and iRECIST, best overall response (BOR), duration of response (DOR), PFS by both RECIST v1.1 and iRECIST, and OS. Biochemical markers (CEA, and CA 19-9 response). The safety of pembrolizumab and olaparib, toxicity grading by grading adverse events (AE) using CTCAE v. 5.0. To note, progression-free survival (PFS) will be analyzed from both the consent date and treatment start date (C1D1) (Reference study POLO defined PFS from the time of randomization not from C1D1, Golan 2019 NEJM).
- Exploratory endpoints: circulating tumor DNA by MSK-ACCESS, second progression-free survival (PFS2) from time of subsequent systemic treatment start post-POLAR to progression on that treatment, and duration of the first-line or second-line treatment prior to POLAR treatment. To also assess genetic signatures and compare clinical outcomes, evaluate reversion mutation, zygosity, plasticity and aneuploidy from tumor and ctDNA, and to assess the role of maintenance treatment with minimally residual disease by the presence of ctDNA and CA 19-9 and its trend prior to treatment.
- Correlative endpoints: Detailed objectives are in Section 4.3 Biomarker Assessments
- Explore HRD genetic signatures.
- Neoantigen surrogates (different mutation types, MHC I and II types, microbiome signatures). Peripheral blood and tumor immunoprofiling, T-cell receptor sequencing, transcriptomic, and proteomic analysis. Differential expression of immunologic gene and tissue protein.
- Intra/intertumoral heterogeneity and correlation of ctDNA to study early detection of resistance emergence.

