Treatment Cycle/Title:	Pre- screening (Visit 1)	1	2	3	4	5	6	7	8	9	Even Cycles (ex. 10, 12, 14 etc.)	Odd Cycles (ex. 11, 13, 15, etc.)	Discontinua tion	Safety Follow-up (in clinic)	Survival Follow- Up (Clinic or phone)
Scheduling Window (Days):	-28		± 3	± 3	±3	At time of Discontinua tion	30 days and 60 days post discontinuation	Every 12 weeks for 5 years							
Directed Physical Examination	Х	x	х	х	Х	х	x	x	x	х	х		Х		
Vital Signs and Weight	Х	х	х	Х	х	х	х	х	х	Х	Х		Х	Х	
ECOG Performance Status	Х	х	х	Х	Х	х	х	Х	х	х	х		Х		
Laboratory Procedure	s/Assessment	s: an	alysi	is per	form	ned b	y LO	CAL	labor	atory					
Pregnancy Test – Urine or Serum □- HCG	Х	х													
PT/INR and aPTT	Х												Х		
CBC with Differential	Х	Х	х	Х	х	х	х	х	Х	Х	Х		Х		
Comprehensive Serum Chemistry Panel	Х	х	х	Х	х	х	х	х	х	Х	Х		х		
CA 19-9, CEA	Х	Х	Х	Х	Х	Х	Х	Х	Х	Х	Х		Х		
HBsAg, IgG anti- HBs, Anti-HCV, HIV screen	х														

Trial Period:	Screening Phase		Trea	itmen	ıt Cy	cles	(21 D	ay C	ycles)	Pembro Q6 Wk		End of Treatment	Post-Treatment	
Treatment Cycle/Title:	Pre- screening (Visit 1)	1	2	3	4	5	6	7	8	9	Even Cycles (ex. 10, 12, 14 etc.)	Odd Cycles (ex. 11, 13, 15, etc.)	Discontinua tion	Safety Follow-up (in clinic)	Survival Follow- Up (Clinic or phone)
Scheduling Window (Days):	-28		± 3	± 3	± 3	At time of Discontinua tion	30 days and 60 days post discontinuation	Every 12 weeks for 5 years							
Urinalysis	Х			Х			Х			Х	Х				
FT3, FT4 and TSH	Х			Х			Х			Х	Х				
EKG	Х			Х			Х			Х	Х				
Efficacy Measurement	s														
Tumor Imaging*	Х				Х			Х			>	(*	Х		
Tumor Biopsies/Archi	Tumor Biopsies/Archival Tissue Collection/Correlative Studies Blood														
Biopsy ^{1, 2, 3}	Х			Х									Х		
Correlative Studies Blood Collection ⁴	Х			Х			Х				>	⟨⁴	Х		
Blood draw to generate plasma for cell free (cf)DNA analysis ⁵	Х			Х			Х				>	〈 5	Х		

Trial Period:	Screening Phase	Treatment Cycles (21 Day Cycles)									Pembro	Q6 Wk	End of Treatment	Post-Treatment	
Treatment Cycle/Title:	Pre- screening (Visit 1)	1	2	3	4	5	6	7	8	9	Even Cycles (ex. 10, 12, 14 etc.)	Odd Cycles (ex. 11, 13, 15, etc.)	Discontinua tion	Safety Follow-up (in clinic)	Survival Follow- Up (Clinic or phone)
Scheduling Window (Days):	-28		± 3	± 3	±3	At time of Discontinua tion	30 days and 60 days post discontinuation	Every 12 weeks for 5 years							

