13.0 CRITERIA FOR OUTCOME ASSESSMENT AND ENDPOINT EVALUABILITY

13.1. Tumor Measurements

Response Evaluation Criteria in Solid Tumors (RECIST) version 1.1 will be used to determine treatment response. Baseline tumor measurements will be performed prior to initiation of therapy. These measurements should be done according to iRECIST (see Appendix 2) ⁵⁴. An estimate of overall objective and subjective response will be made and recorded at the end of treatment at 8 weeks after the last infusion. Since it is expected that immune activity would lead to tumor flare, the restaging CT scans may be repeated 8 weeks later based on irRECIST and the designation of iCR, iPR, iSD, iUPD, or iCPD will be made at that time. Best overall response will be used.

- **13.1.2.** Disease control rate (DCR): DCR is defined as the percentage of patients who have achieved complete response, partial response, and stable disease to the study treatment.
- **13.1.3.** Overall response rate (ORR): ORR is defined as the percentage of patients who have achieved complete response and partial response to the study treatment.
- **13.1.4. Best Overall Response (BOR):** BOR is defined as the best response recorded from the start of the study treatment until the disease progression/recurrence.
- **13.1.5.** Durable response rate (DRR): DRR is defined as the percentage of patients who had achieved continued disease responses (CR and PR) for more than 6 months.
- **13.1.6.** Durable disease control rate (DDCR): DDCR is defined as the percentage of patients who had achieved continued disease controls (CR, PR, and SD) for more than 6 months from the time from the initiation of study treatment.
- **13.1.7. Additional Assessments.** All patients will have a baseline tumor marker assessment and testing of tumor markers at the designated follow-up time points. Changes in serial tumor marker measurements, in those patients who have baseline elevations, will be utilized as a surrogate marker of clinical response, stable disease or disease progression and reported as such.
- **13.1.8. Patients without residual disease:** For patients whose primary tumor or metastatic disease has been removed or successfully treated, respectively, prior to entry into this trial, progression free survival will be evaluated based on duration of relapse-free survival.
- **13.1.9. Progression free survival (PFS):** PFS is defined as the time from the initiation of study treatment to radiographic progression or death.

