14.0 BIOSTATISTICS

This is a phase 2, open-label, non-randomized study evaluating the novel combination of pembrolizumab and olaparib (POLAR) in three cohorts of metastatic PDAC s with homologous recombination deficiency (HRD) in the first-line or second-line on-platinum maintenance setting, two of which are genomically enriched and one is identified by platinum sensitivity. The primary objective of the study is to determine both the 6-month PFS rate by RECIST v1.1 as well as the objective response rate (ORR, CR+PR) by iRECIST for this combination. Both factors will be considered for purposes of sample size determination as follows and a two-stage design will be employed. The secondary endpoints of this study are overall survival (OS), progression-free survival (PFS) by both RECIST v1.1 and iRECIST, disease control rate (DCR) by both RECIST v1.1 and iRECIST, CA 19-9, and CEA response. Progression-free survival (PFS) will be analyzed from both the consent date and treatment start date (C1D1), separately, due to the maintenance trial design. Exploratory scientific correlates include assessments of HRD genetic mutational signatures, neoantigens, immunogenic tumor microenvironment, clonal evolutionary dynamics to study heterogeneity, andresistance mechanism to POLAR. Exploratory endpoints will also include second progressionfree survival (PFS2) from time of subsequent systemic treatment start post-POLAR to progression on that treatment as well as assess duration of the first-line or second-line treatment prior to POLAR treatment. Exploratory endpoints will also assess genetic signatures and compare clinical outcomes, evaluate reversion mutation, zygosity, plasticity and aneuploidy from tumor and ctDNA, and to assess the role of maintenance treatment with minimally residual disease by the presence of ctDNA and CA 19-9 and its trend prior to treatment.

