Wilcoxon rank sum test will be used to assess associations between genetic and transcriptomic signatures at baseline with response while Cox regression will be used to assess associations with PFS and OS. These analyses will be conducted separately for each cohort acknowledging the exploratory nature of these analyses particularly for Cohorts B and C which have limited sample size. Changes between baseline and after treatment in neoantigen induction, TME, and immunomodulatory targets will be summarized descriptively using medians and interquartile range for each cohort separately. To understand the resistance mechanisms, post-treatment changes (4-6 weeks and at progression) of tumor samples and circulating tumor DNA (MSK-ACCESS) from baseline will be associated with response using Wilcoxon rank sum test while Cox regression will be used for PFS and OS outcomes. Finally, in selected patients with viable organoids available from IRB# 15-149 prior to enrollment to POLAR trial, we will concurrently evaluate the response of organoid to POLAR in real time as participants are treated in parallel. Dr. [name] will oversee this part. PFS2 will be estimated using the Kaplan-Meier method. Associations between genetic mutations (HRD and non-HRD) and outcome will be assessed using Fisher's exact test for response and log-rank test for survival outcomes. Biomarkers (reversion mutation, zygosity, plasticity, aneuploidy from tumor, and circulating tumor DNA) will be summarized using proportions. Presence of circulating tumor DNA and levels of CA 19-9 prior to treatment at time points prior to consent and between the consent and start date will be graphically summarized at each timepoint.

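### PFS2 is written with progression on the next therapy as its only event, so a Kaplan-Meier estimate that follows the text censors deaths and can only err upward

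*Protocol*

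**What the plan says.** PFS2 is described three times in the protocol, each time with the same time origin and the same single event.

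- Section 2.0, Exploratory Objectives: "To assess second progression-free survival (PFS2) from time of subsequent systemic treatment start post-POLAR to progression on that treatment".
- Section 4.1, Study Endpoints: "second progression-free survival (PFS2) from time of subsequent systemic treatment start post-POLAR to progression on that treatment".
- Section 14.0, opening paragraph: "from time of subsequent systemic treatment start post-POLAR to progression on that treatment".

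The only analysis instruction is in Section 14.0 under exploratory objectives: "PFS2 will be estimated using the Kaplan-Meier method". Nothing says how a death without progression is treated.

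Ordinary PFS is defined in 13.1.9: "PFS is defined as the time from the initiation of study treatment to radiographic progression or death". Its clock starts at study treatment, so it does not define PFS2.

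After treatment ends, Table 9 (Section 11.1) has a survival follow-up column, by clinic or phone, scheduled "Every 12 weeks for 5 years". Survival status and medication review are marked there. Tumor imaging is not marked after the discontinuation visit.

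**The concern.** The endpoint is named as a form of progression-free survival, but the event written for it is progression alone. Kaplan-Meier needs every patient's exit classed as an event or as censored. Under the written definition, death on the next therapy without progression is not an event, so it is censored. That treats the patient as if he or she would have gone on to progress at the same rate as those still alive. In metastatic pancreatic cancer this is hard to defend, because death and progression are closely linked.

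At stake is the meaning of one exploratory estimate. Two analysts with the same data could report different PFS2 medians, one following the name and the other the definition. The one who follows the definition reports the longer figure.

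**Working it through.** **1. No figure to reproduce.** The protocol states no median, rate, sample size or power for PFS2. What can be checked is the direction of the effect and its size over an assumed range.

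**2. Direction.** Suppose each patient leaves the risk set on the date of progression, death or last contact. Whether death is an event or a censoring, the risk sets are then the same. Only the count of events *d* in each Kaplan-Meier factor (1 − *d*/*n*) changes. Counting deaths can raise *d* but never lower it, so the progression-only curve lies at or above the progression-or-death curve at every time. This needs no assumption about hazards. It does assume that a censored death leaves the risk set on the date of death; the protocol sets no other date.

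**3. Size.** All inputs here are assumed; none is in the protocol.

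- λp is the hazard of progression on the next therapy and λd the hazard of death without progression, both constant and independent.
- *s* is the share of first events that are deaths, so λd = λp × s/(1 − s).
- Median with deaths censored: ln 2/λp.
- Median with deaths counted: ln 2/(λp + λd) = (1 − s) × ln 2/λp.
- Ratio of the two: 1/(1 − s), whatever the starting median.

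For an illustrative progression-only median of 4 months, the 6-month rate with deaths censored is exp(−6 × ln 2/4) = 35.4%. With deaths counted:

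| Assumed s | Median, deaths counted (months) | Ratio of medians | 6-month rate, deaths counted |
|---|---|---|---|
| 10% | 3.6 | 1.11 | 31.5% |
| 20% | 3.2 | 1.25 | 27.3% |
| 30% | 2.8 | 1.43 | 22.6% |
| 40% | 2.4 | 1.67 | 17.7% |

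For s = 20%: λp = 0.693/4 = 0.173 per month, λd = 0.173 × 0.2/0.8 = 0.043, and the median is 0.693/0.217 = 3.2 months.

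**4. Small-sample check.** In 4,000 simulated samples of 25 patients (an assumed number starting a next therapy), with s = 20% and a 4-month progression-only median, the middle Kaplan-Meier median was 4.0 months with deaths censored and 3.2 with deaths counted. This agrees with the formula.

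**5. Reach.** The Cohort A two-stage rules use only 6-month PFS and ORR. Exact binomial calculation reproduces the stated figures: for PFS, type I error 0.028 at 53% and power 0.806 at 77%; for ORR, 0.020 at 20% and 0.809 at 43%. PFS2 enters none of these.

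**The case against.** The strongest reply is that this is an incomplete one-line description, not a chosen progression-only analysis. The protocol never says that deaths are censored. The name contains the word survival, and the objective and endpoint lists do not spell out death for ordinary PFS either; it appears only in 13.1.9. Detailed censoring rules for an exploratory endpoint are often left to a statistical analysis plan.

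Part of this stands: death may well have been intended, and no reader should conclude that the sponsor decided to censor deaths. But the protocol does more than stay silent. It fixes an origin, an event and an estimator, and repeats the origin and event in three places. Ordinary PFS has a definition elsewhere that supplies death; PFS2 has none, because 13.1.9 starts from a different time. If death was intended, adding it costs nothing.

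It can also be said that the PFS2 wording does not require radiographic progression, so clinical progression might count. That would lower the share of deaths without progression, but it would not settle how the remaining deaths are handled.

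A reader might infer several stronger points that the documents do not support:

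- **That leaving out patients who never start a next therapy is a hidden error.** It follows openly from the stated time origin, and OS from the start of treatment covers everyone. It calls for an accurate label and a count.
- **That many patients will die without documented progression.** Imaging is not scheduled after discontinuation, but no rate is given.
- **That the result would be used to show that POLAR spares later treatment.** PFS2 has no hypothesis, comparator or decision rule here.
- **That a C1D1-based version for all patients could be added with no new data.** Table 9 schedules no second-progression assessment in follow-up.

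**Conclusion.** The point holds as a defect in the written event definition. Taken literally, all three statements of PFS2 make death without progression a non-event, and the Kaplan-Meier estimate then lies at or above the progression-or-death estimate. The direction follows from the definition, given censoring on the date of death.

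The size is not known. The range of 1.11 to 1.67 for the median rests on an assumed death share of 10% to 40% and on constant, independent hazards. It illustrates what could happen and is not an estimate for this trial.

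The consequence is small: one exploratory, descriptive endpoint, drawn from at most 63 patients, with no bearing on the Cohort A design or on any secondary endpoint.

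**What to change.** In Sections 2.0, 4.1 and 14.0, define the PFS2 event as progression on the next systemic therapy or death from any cause, whichever comes first. Describe the result as PFS on next therapy among patients who start one, and report beside it how many patients never do.

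The cost is a short wording change in three places and a somewhat shorter reported PFS2. Deaths are already captured through survival status in the 12-weekly follow-up. The date of progression on the next therapy is needed for PFS2 as it stands, so counting deaths adds nothing to collect. Keep the present time origin: a version measured from C1D1 would be a different endpoint, and second-progression dates are not scheduled in follow-up.
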